3.4.7.3 Pharmacokinetic analyses

Blood MP1032 concentration-time data for both MP1032 treatment groups in the PKS will be listed, summarized and displayed graphically, including the nominal and actual blood sampling time relative to the corresponding IMP administration time.

Summary statistics of MP1032 levels by nominal sampling time will be provided with following summary statistics for each nominal sampling time: geometric mean, geometric standard deviation (re-transformed standard deviation of the logarithms) and geometric coefficient of variation (CV), arithmetic mean, standard deviation, CV, minimum, median, maximum value and the number of measurements.

Generally, summary statistics will only be presented if at least 6 quantifiable outcomes are available, i.e. if at least 6 concentrations were above the lower limit of quantification (LLQ). For the calculation of the summary statistics, pre-dose/through levels below LLQ will be substituted by zero and post-dose levels will be substituted by LLQ/2.

Individual and mean concentration versus time curves of M1032 concentration (using the actual sampling times for individual plots and the planned sampling times for mean plots) will be plotted by treatment. Plots of geometric means on linear concentration scale and of geometric means on semilogarithmic scale will be presented.

Based on the concentration-time data the following non-compartmental analysis (NCA) parameter will be derived for both visits separately:

- C_{\max} : Maximum MP1032 concentration observed
- t_{\max} : Time point (effective) at which the C_{\max} is observed
- $AUC_{(0,t)}$: Area under the concentration-time curve (AUC) up to the last quantifiable sample drawn.

The AUC will be approximated using the trapezoid formula and calculated with the effective time points 0, ... t. The pre-dose value will be defined as 0 for calculation of $AUC_{(0,t)}$ and missing intermediate concentrations will be excluded from the calculations.

Pharmacokinetic characteristics will be listed and summarized by the statistics mentioned above in the PKS for each treatment and visit. The parameter t_{\max} will be described utilizing minimum, maximum and median.

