3.5.1 Missing data

A description of missing data will be provided in the clinical study report.

For the evaluation of success rates of the primary efficacy variables PASI and PGA missing PGA assessments and/or any parts of the PASI assessments will be evaluated as failure to achieve improvement.

For descriptive analyses of PASI, PGA and BSA the last observation carried forward (LOCF) principle will be applied to impute the missing assessments, up to the Day 84 visit. Follow-up assessments will not be imputed.

Sensitivity of the primary efficacy analyses will be evaluated applying PP analyses.

Regarding incomplete recordings for adverse events the following rules apply:

- For start and stop dates no imputation will be applied. If any, start or stop date, is not complete, but required for the classification, i.e. the occurrence of the AE is not explicitly reported as occurring prior first dose (see eCRF), the AE will be considered treatment emergent.
- Missing assessments of severity, intensity and causal relationship to the IMP will be reported as a separate category.

For the determination of the number of years from start of psoriasis to the screening visit missing starting days will be imputed by the first day of month and missing months will be imputed by the first month (January) of the year.

For concomitant therapies (see section 3.2.2.4) incomplete dates will not be imputed. If an incomplete start or stop date does not allow for the classification as prior and/or concomitant therapy - despite of information in eCRF if taken/used prior to first dosing and/or if ongoing at first dosing - the treatment will be reported as prior and as concomitant therapy.

Pharmacokinetic data below LLQ will be replaced as described in 3.4.7.3 for descriptive statistics and for the derivation of $AUC_{(0,t)}$. Missing pre-dose levels will be imputed by zero. Missing intermediate samples, i.e. missing values in between non-missing levels (quantifiable or substituted by LLQ/2) will be imputed by linear interpolation between the last preceding and the next following available value. The last value will be imputed by LLQ/2, if missing.

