Mean		--	XXX.X	XXX.X	XXX.X	XXX.X	--	XXX.X	XXX.X	XXX.X	XXX.X
SD		--	XXX.X	XXX.X	XXX.X	XXX.X	--	XXX.X	XXX.X	XXX.X	XXX.X
Median		--	XXX.X	XXX.X	XXX.X	XXX.X	--	XXX.X	XXX.X	XXX.X	XXX.X
Minimum		--	XXX.X	XXX.X	XXX.X	XXX.X	--	XXX.X	XXX.X	XXX.X	XXX.X
Maximum		--	XXX.X	XXX.X	XXX.X	XXX.X	--	XXX.X	XXX.X	XXX.X	XXX.X

¹ Time since morning dose [min]

² Relative pre-dose time is set to 0 for derivations.

Source data: <DATASET> <DATE>

Program: <SAS PROGRAM> <DATE>

Table 14.8.4: PK data – PK data – Relative blood sampling time (PKS) - MP1032 300 mg bid

Analog to Table 14.8.3 for treatment MP1032 300 mg bid

Figure 14.5: PK data – Profile plots for subject's MP1032 concentration over time (PKS) - MP1032 150 mg bid

Day 1

About 10 lines (=subjects)
x-axis: actual time points
y-axis linear scaled

Week 12 / EoT

About 10 lines (=subjects)
x-axis: actual time points
y-axis linear scaled

Source data: <DATASET> <DATE>
Program: <SAS PROGRAM> <DATE>

Figure 14.6: PK data – Profile plots for subject's MP1032 concentration over time (PKS) - MP1032 300 mg bid

Analog to Figure 14.5 for treatment MP1032 300 mg bid.

Figure 14.7: PK data – Semi-logarithmic scaled profile plots for subject's MP1032 concentration over time (PKS) - MP1032 150 mg bid
Analog to Figure 14.5 with logarithmic scaled y-axis

Figure 14.8: PK data – Semi-logarithmic scaled profile plots for subject's MP1032 concentration over time (PKS) - MP1032 300 mg bid
Analog to Figure 14.5 for treatment MP1032 300 mg bid with logarithmic scaled y-axis

Figure 14.9: PK data – Mean profiles for treatments over time (PKS)

Analog to Figure 14.5, the lines represent geometric means of MP1032 concentrations over nominal time points, linear scale for y-axis.
NOTE: A line in this figure will only be generated if at least 6 subjects in the respective treatment arm have at least one concentration higher than LLQ.

Figure 14.10: PK data – Semi-logarithmic scaled mean profiles for treatments over time (PKS)

Analog to Figure 14.5, the lines represent geometric means of MP1032 concentrations over nominal time points, logarithmic scale for y-axis.
NOTE: A line in this figure will only be generated if at least 6 subjects in the respective treatment arm have at least one concentration higher than LLQ.

Table 14.8.5: Non-compartment parameters – C_{max} [ng/mL] (PKS) - MP1032 150 mg bid
(Part 1 of 1)

C_{max} [ng/mL]	MP1032 150 mg bid (N = XX)	
	Day 1	Week 12 / EoT
Subject ID		
XXX	XXX.X	XXX.X
N	XX	XX
Geom. Mean	XXX.X	XXX.X

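### The SAP's zero rules for pre-dose PK samples do not separate Day 1 from Week 12, so Week 12 trough geometric statistics can be undefined, missing troughs become zero and, read literally, measured troughs drop out of the AUC

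*SAP*

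**What the plan says.** SAP 3.2.2.3 schedules PK blood samples before the morning dose and at 15, 30, 60 and 120 minutes after it, on Day 1 and again on Day 84. SAP 3.4.7.3 derives the non-compartmental parameters separately for the two visits.

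For every nominal sampling time, SAP 3.4.7.3 asks for "geometric mean, geometric standard deviation (re-transformed standard deviation of the logarithms) and geometric coefficient of variation (CV"), alongside arithmetic statistics. It adds that "summary statistics will only be presented if at least 6 quantifiable outcomes are available".

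Three rules put a zero in the pre-dose position:

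- **Below LLQ (SAP 3.4.7.3):** "pre-dose/through levels below LLQ will be substituted by zero and post-dose levels will be substituted by LLQ/2".
- **Missing (SAP 3.5.1):** "Missing pre-dose levels will be imputed by zero".
- **AUC (SAP 3.4.7.3):** "The pre-dose value will be defined as 0 for calculation of" AUC(0,t).

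In the SAP Appendix, the notes to Figures 14.9 and 14.10 (geometric mean profiles, linear and logarithmic axis) allow a line only "if at least 6 subjects in the respective treatment arm have at least one concentration higher than LLQ".

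**The concern.** The two pre-dose samples are different quantities. On Day 1 the patient has taken no drug, so zero is the known value. On Day 84 the sample is a trough after 12 weeks of twice-daily dosing, and zero is then an assumption about a patient on treatment. The rules make no distinction, and the first one names trough levels explicitly, so Week 12 is covered.

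There are three consequences at Week 12. A zero cannot enter a statistic built on logarithms. A missing trough acquires a value that nobody measured. Taken at its word, the AUC sentence discards a trough that was measured.

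Systemic exposure over 12 weeks of treatment is a stated secondary objective (SAP Table 1). The Week 12 pre-dose sample is the only one taken to show what remains from the previous dose.

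**Working it through.** The plan states no figure of its own here, so the check follows each rule through.

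**Inputs from the documents.** Sampling is at 0, 15, 30, 60 and 120 min. The table threshold is 6 quantifiable values per time point. There are about 10 patients per active arm (SAP Appendix, Figure 14.5; also 30 / 3 = 10). **Not given, so assumed as ranges:** LLQ, half-life, trough level, and the share of Week 12 troughs that are quantifiable.

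**1. Geometric statistics.** Geometric mean = exp(mean of log C); geometric SD = exp(SD of log C). With any C = 0, log C does not exist. For n = 10 and X quantifiable troughs:

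- X = 0 to 5: the table suppresses the statistics.
- X = 6 to 9: the statistics are required but undefined.
- X = 10, none missing: they compute normally.

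With X ~ Binomial(10, p), the chance of the undefined case is the sum of P(X = x) for x = 6 to 9:

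| Assumed share p | Suppressed | Undefined | Computable |
|---|---|---|---|
| 0.3 | 95% | 5% | 0% |
| 0.5 | 62% | 38% | <1% |
| 0.7 | 15% | 82% | 3% |
| 0.8 | 3% | 86% | 11% |
| 0.9 | <1% | 65% | 35% |
| 1.0 | 0% | 0% | 100% |

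This counts below-LLQ values only. Once 6 troughs are quantifiable, a single missing trough set to zero has the same effect.

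Illustration with LLQ = 1, nine assumed troughs (2, 2.5, 3, 3, 3.5, 4, 4.5, 5, 6) and one below LLQ:

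| Handling of the tenth value | Geometric mean | Geometric SD |
|---|---|---|
| Zero (SAP) | collapses to 0 | undefined |
| LLQ/2 | 2.90 | 2.01 |
| Dropped | 3.53 | 1.42 |

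**2. Missing troughs.** Take the same nine values, with the tenth missing. Left missing, the mean is 33.5 / 9 = 3.72. Set to zero, it is 33.5 / 10 = 3.35. The ratio is 9/10, a 10% reduction for one missing trough of ten, whatever the values.

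**3. AUC.** In the linear trapezoid, the first interval contributes 15 x (C0 + C15) / 2. Replacing C0 by 0 removes 15 / 2 x C0 = 7.5 min x C0. Under an assumed one-compartment steady-state model (12-hour interval, absorption half-life 10-20 min):

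| Assumed half-life | Loss in Week 12 AUC(0-120) | Week 12 / Day 1 AUC ratio, true C0 | Same ratio, C0 = 0 |
|---|---|---|---|
| 2 h | 0.2% | 1.02 | 1.02 |
| 6 h | 2.0-2.2% | 1.39-1.47 | 1.37-1.43 |
| 12 h | 3.6-3.8% | 2.17-2.37 | 2.09-2.28 |

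A separate check with three assumed profile shapes gives 0.4-0.6% at a trough/Cmax ratio of 0.05, 1.6-2.3% at 0.2, and 3.9-4.9% at 0.5.

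**4. Figures.** The table threshold applies per time point. The figure note counts patients with any one quantifiable value. If that note alone governed, a time point with every sample below LLQ would be blank in the table but plotted. A post-dose point would sit at LLQ/2. A pre-dose point would be zero, which the log axis of Figure 14.10 cannot show.

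**The case against.** **The AUC sentence may concern time, not concentration.** The footnote to shell Table 14.8.3 sets the relative pre-dose time to 0. This reading is weak. SAP 3.4.7.3 says value, and the sentence before it has already fixed the time points. SAP 3.5.1 already covers below-LLQ and missing pre-dose values, so only a quantifiable pre-dose concentration is left for this rule to change. The sentence still needs clarifying.

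**The zero imputation may be meant for the AUC only.** SAP 3.5.1 does not say so, and the sentence before it covers both descriptive statistics and the AUC.

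**The data are not lost.** This stands. Shell Table 14.8.1 lists each patient's trough with counts below and above LLQ, and Figures 14.5 to 14.8 plot individual profiles.

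**The setting is modest.** This also stands. It is descriptive PK in about 30 patients of an exploratory trial, and efficacy and safety conclusions are untouched.

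A reader might infer four stronger things that the documents do not support:

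- *That the Week 12 geometric statistics can never be computed.* The failure is conditional, as shown above.
- *That the AUC rule hides accumulation.* A doubling remains a doubling in the ratios above, because the four post-dose samples and Cmax keep their accumulated levels.
- *That the trough would be overstated up to 3-fold.* This assumes that software silently drops zeros, which the SAP does not say. It also needs 4 of 10 below LLQ with a quantifiable geometric mean of 8 x LLQ: (8 / 0.5)^(4/10) = 3.03. One of ten gives 1.15 to 1.32 for means of 2 to 8 x LLQ. The comparator, LLQ/2, is itself a convention.
- *That Figures 14.9 and 14.10 will plot suppressed points.* The note gives a necessary condition for drawing a line, not a sufficient one. The per-time-point rule may still govern the plotted means.

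**Conclusion.** The rules are wrong as written for Week 12. They require statistics that do not exist whenever at least 6 troughs are quantifiable and at least one is below LLQ or missing. With about 10 patients per arm and independent values, that is the likely outcome over much of the middle range of quantifiable shares: 38% at 0.5, 86% at 0.8 and 65% at 0.9. Each missing trough imputed as zero takes about 10% off the arithmetic mean. Read literally, the AUC rule understates Week 12 AUC(0-120) by 7.5 min x C0. That is about 0.2-4% under the assumed half-lives of 2-12 h, and up to about 5% in the assumed profiles, so it is small.

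Whether any of this matters in practice cannot be judged from the documents, which give no LLQ, half-life or trough level. If every Week 12 trough is measured and below LLQ, the tables and the AUC are unaffected. The figure thresholds need clarifying and are not shown to be in error.

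**What to change.** In SAP 3.4.7.3 and 3.5.1:

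- Limit all three zero rules to the Day 1 pre-dose sample.
- For the Week 12 pre-dose sample, substitute LLQ/2 for below-LLQ values in all summary statistics (geometric and arithmetic) and in the AUC, as for post-dose samples.
- Leave missing Week 12 troughs missing in the summaries.
- Use the measured Week 12 trough as C0 in the Week 12 AUC. Where it is missing, keep the AUC with C0 = 0 and flag it as a slight underestimate. Dropping the patient would lose about 10% of the arm to protect a term of a few percent.
- State that the rule of at least 6 quantifiable values per time point also governs the geometric means plotted in Figures 14.9 and 14.10.

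The cost is SAP wording and a few lines of code before database lock. No new samples or data are needed.

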3.4.7.4 Other safety analyses

Vital signs will be summarized descriptively, including changes from baseline. Shift tables of normal and abnormal outcomes and incidence of clinically significant vital sign parameter will be presented.

Findings in the physical examination will be listed.

3.4.7.5 Extent of exposure to study drug

The overall extent of exposure to study drug will be summarized by

- total number of applications =
planned applications – # missed applications + # overdose applications
- total number of dosed capsules =
6 * # planned applications – # missed capsules + # overdose capsules
- average number of capsules per application =
total number of dosed capsules / total number of applications

- duration of the treatment (days of treatment) =
duration from first dose to last dose in days, start and end day included.
- average number of capsules per day =
total number of dosed capsules / days of treatment
- % exposure =
 $100 * \text{total number of dosed capsules} / (84 * 2 * 6)$

For each treatment descriptive statistics will be given. Duration of treatment will additionally be presented by a frequency table for categorized numbers of days (less than 26 days, 26 to 53 days, 54 to 83 days, 84 days and more) and % exposure will be presented by exposure of less than 80% and 80% and more. .

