5.4.2 Identity of investigational medicinal products

Details of the IMPs are given in the table 3.

Table 3: Identity of investigational medicinal products:

Generic name/brand name/INN	Verum	Placebo
Formulation	Hard gelatin capsules, size 3 The mixture (995 parts mannitol and 5 parts colloidal anhydrous silica) is well known and described in compendia (German: Neues Rezepturformularium, Monographie Nr. S. p. 38.). At least 25% of the mass of the contents are active ingredient. Placebo capsules constituted only of the excipients described above.	
Active ingredient	MP1032 5-Amino-1,4-dioxo-1,2,3,4-tetrahydropthalazine-3-id, sodium salt	n.a.
Amount per unit	containing 50 mg MP1032 for oral administration	n.a.
Primary packaging	Blister	Blister
Storage	room temperature (15 – 25 °C)	room temperature (15 – 25 °C)
Manufacturers	CCI ██████████ ██████████	CCI ██████████ ██████████

All IMPs will be labeled according to the requirements of local law and legislation. A copy of the labels will be filed in the trial master file (TMF).

All IMPs used during the trial will be stored at the trial center in accordance with instructions given, and will be inaccessible to unauthorized personnel.

Missing a treatment

If the patient misses a dose, and remembers the dose within 6 hours of scheduled dosing, he/she may take it. If it has been more than 6 hours since the planned dose time, the patient should skip the dose. All missing doses should be documented by the patient in the diary. However, all administrations will take place with at least 8 hours between the dosings.

Overdose

The risk of overdosing in general in this trial is considered to be low due to the maximum dose that each patient can receive via six capsules being 150 mg, 300 mg MP1032 or Placebo. Nevertheless, unintentional administration of any dose that deviates from the scheduled regimen will be documented and reported by site staff via eCRF. In case of overdose symptomatic

treatment should be provided as indicated and a safety blood analysis should be performed. The Sponsor should be informed immediately.

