2.3 Study plan

Table 2 Trial flow chart

Trial Period	Screening	Treatment phase				Follow-up	Unscheduled visit ^g	
Day	(Day - 28 to -3)	Day 1	Day 28 (±2 days)	Day 56 (±2 days)	Day 84 (±5 days)	Day 112 (±2 days)		
Procedure	Visit Number	1	2	3	4	5	6	Unscheduled
Informed consent		X						
In-/exclusion criteria		X	X					
Demographics/medical history		X						
Physical examination		X	X			X	X	
Height, body weight, BMI		X						
Smoking history/ alcohol consumption		X						
Vital signs		X	X	X	X	X	X	
Pregnancy test in female patients ^a		X	X ^b			X		
Safety laboratory, incl. urine dipstick		X	X	X	X	X	X	X
HIV, Hepatitis		X						
Randomization			X					
Localization of photographic documentation test field ^c			X					
Photographic documentation ^c			X	X	X	X	X	
PK sample ^d			X			X		
PASI		X	X	X	X	X	X	
PGA		X	X	X	X	X	X	
BSA		X	X	X	X	X	X	
Dispensing of IMP			X	X	X			
IMP administration ^e			X	X	X	X		
Diary dispensing			X	X	X			
Drug return / accountability				X	X	X		
Diary return and check				X	X	X		
Prior and concomitant therapy		X	X	X	X	X	X	X
Adverse events ^f		X	X	X	X	X	X	X

- a) A serum pregnancy test will be done for all women at screening and urine test for all other visits.
- b) A urine pregnancy test on Day 1 will be performed prior to the first administration of IMP for all women.
- c) Only performed in a subgroup of approx. 2 sites (approx. 30 patients); on Day 1 Photographic documentation will be performed prior to the first administration of IMP
- d) Only performed in a subgroup of approx. 4 sites (approx. 30 patients); on Day 1 and Day 84 first PK sample will be performed prior to the first administration of IMP. PK samples will be collected before IMP administration, and 15, 30, 60 and 120 minutes after administration of IMP.
- e) IMP administration will start on Day 1 after randomization and will continue as self-administration by trial patients at home until Day 84. Patients included in the PK analysis will administrate the first treatment (Day 1) at the site. All patients will administrate the last treatment (Day 84) at the sites.
- f) AE reporting starts after the signature of informed consent form and finishes at the End of Study Follow-Up Visit.
- g) Perform assessments which are relevant to the reason for the unscheduled visit (e.g. Photographic documentation, Lab analysis, PASI, PGA, BSA, etc.).

3 Statistical and analytical procedures

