3.3 Analysis populations

3.3.1 Efficacy populations

Intent-To-Treat (ITT)

The full-analysis-set (FAS) will include all randomized patient who received at least one dose of IMP, and had at least one post-baseline assessment. The intention-to-treat (ITT) analysis will be based on the FAS. The FAS is considered primary analysis set for the efficacy analysis.

Per-Protocol (PP)

The valid-cases-set (VCS) will include all patients from the FAS, who completed the assessments of the co-primary endpoints without any protocol violation interfering with the precise evaluation of treatment efficacy and with sufficient exposure to IMP, i.e.

- who completed the visit 5 (Day 84) assessments of PASI and PGA;
- who did not take any prohibited concomitant medications up to the visit 5 (Day 84).

During the blind data review meeting (BDRM) concomitant medications will be reviewed considering timing, duration of concomitant treatment, and influence on the efficacy assessments to determine prohibited medication usage that warrants exclusion from the VCS;

- who were compliant with the dosing regimen. A subject will be considered compliant, if the subject administered $\geq 80\%$ of the planned capsules.

Subjects who prematurely discontinue the treatment due to an adverse event at least possibly related to IMP will not be excluded from the VCS.

Prior to breaking the blind, other additional criteria may be added to the list to accommodate for unforeseen events that occurred during the conduct of the trial that result in noteworthy study protocol violations.

The per-protocol (PP) analysis will be based on the VCS. Primary efficacy endpoints will be evaluated on VCS to assess the sensitivity.

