3.4.5 Compliance

The % treatment compliance will be determined as the number of performed treatment applications in relation to the planned applications within the individual subjects treatment phase:

- total number of applications =
planned applications – # missed applications + # overdose applications
- % treatment compliance =
100 * total number of applications / # planned applications

The % dosing compliance will be determined as the number of dosed capsules in relation to the number of planned capsules within the individual subjects treatment phase:

- total number of dosed capsules =
$$6 * \# \text{ planned applications} - \# \text{ missed capsules} + \# \text{ overdose capsules}$$
- % dosing compliance =
$$100 * \text{total number of dosed capsules} / (6 * \# \text{ planned applications})$$

The % treatment compliance and % dosing compliance will be summarized by descriptive statistics and frequency counts will be given for sufficient ($\geq 80\%$) and insufficient ($< 80\%$) compliance.

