Treatment duration³			
N	XX	XX	XX
Mean ± SD	XX.X ± XX.X	XX.X ± XX.X	XX.X ± XX.X
Median	XX.X	XX.X	XX.X
Min , max	XX , XX	XX , XX	XX , XX
Less than 28 days	XX (XXX.X%)	XX (XXX.X%)	XX (XXX.X%)
29 to 56 days	XX (XXX.X%)	XX (XXX.X%)	XX (XXX.X%)
57 to 84 days	XX (XXX.X%)	XX (XXX.X%)	XX (XXX.X%)
More than 84 days	XX (XXX.X%)	XX (XXX.X%)	XX (XXX.X%)
Average number of capsules per application⁴			
N	XX	XX	XX
Mean ± SD	XX.X ± XX.X	XX.X ± XX.X	XX.X ± XX.X
Median	XX.X	XX.X	XX.X
Min , max	XX.X , XX.X	XX.X , XX.X	XX.X , XX.X
Average number of capsules per day⁵			
N	XX	XX	XX
Mean ± SD	XX.X ± XX.X	XX.X ± XX.X	XX.X ± XX.X
Median	XX.X	XX.X	XX.X
Min , max	XX.X , XX.X	XX.X , XX.X	XX.X , XX.X
% Exposure⁶			
N	XX	XX	XX
Mean ± SD	XXX.X ± XXX.X	XXX.X ± XXX.X	XXX.X ± XXX.X
Median	XXX.X	XXX.X	XXX.X
Min , max	XXX , XXX	XXX , XXX	XXX , XXX
Insufficient (< 80%)	XX (XXX.X%)	XX (XXX.X%)	XX (XXX.X%)
Sufficient (≥ 80%)	XX (XXX.X%)	XX (XXX.X%)	XX (XXX.X%)

¹ Total number of applications = # planned applications – # missed applications +# overdose applications

² Total number of dosed capsules = 6 * # planned applications – # missed capsules” + # overdose capsules

³ Treatment duration = date of last dose – date of first dose + 1.

⁴ Average number of capsules per application = # dosed capsules / # applications

⁵ Average number of capsules per day = # dosed capsules / days of treatment

⁶ % Exposure = 100 * # dosed capsules / (84 * 2 * 6)

Table 14.5.1: Overview on adverse events (SES)
(Part 1 of 1)

Adverse events Count¹ / Incidence² (Incidence rate%³)	MP1032 300 mg bid (N = XX)	MP1032 150 mg bid (N = XX)	Placebo bid (N = XX)
TEAEs ⁴	XXX / XX (XXX X%)	XXX / XX (XXX X%)	XXX / XX (XXX X%)
TEAEs by intensity ⁵			
Severe	XXX / XX (XXX.X%)	XXX / XX (XXX.X%)	XXX / XX (XXX.X%)
Moderate	XXX / XX (XXX.X%)	XXX / XX (XXX.X%)	XXX / XX (XXX.X%)
Mild	XXX / XX (XXX.X%)	XXX / XX (XXX.X%)	XXX / XX (XXX.X%)
TEAEs by relation to the IMP ⁵			
Certain	XXX / XX (XXX.X%)	XXX / XX (XXX.X%)	XXX / XX (XXX.X%)
Probable	XXX / XX (XXX.X%)	XXX / XX (XXX.X%)	XXX / XX (XXX.X%)
Possible	XXX / XX (XXX.X%)	XXX / XX (XXX.X%)	XXX / XX (XXX.X%)
Unlikely	XXX / XX (XXX.X%)	XXX / XX (XXX.X%)	XXX / XX (XXX.X%)
Not related	XXX / XX (XXX.X%)	XXX / XX (XXX.X%)	XXX / XX (XXX.X%)
Serious TEAEs	XXX / XX (XXX.X%)	XXX / XX (XXX.X%)	XXX / XX (XXX.X%)
TEAEs leading to study discontinuation	XXX / XX (XXX.X%)	XXX / XX (XXX.X%)	XXX / XX (XXX.X%)

¹ Count of AEs reported

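### Treatment-duration bands differ between the SAP text and its table shell, and the SAP is inconsistent on whether overdose capsules offset missed ones in the 80% compliance rule

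*SAP*

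**What the plan says.** **Duration.** SAP 3.4.7.5 asks for a frequency table with the bands "less than 26 days, 26 to 53 days, 54 to 83 days, 84 days and more". The shell for it, SAP Appendix Table 14.4.23, starts at "Less than 28 days", continues with 29–56 and 57–84, and ends with "More than 84 days". Its footnote defines "Treatment duration = date of last dose – date of first dose + 1". On the final dose, a flow-chart footnote in SAP 2.3 says "All patients will administrate the last treatment (Day 84) at the sites".

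Two other places bear on what counts as 12 weeks. Table 14.1.3 treats a patient as completing Week 12 if the PASI visit falls on study days 80 to 91 and exposure is at least 80% of plan; Day 79 or earlier, or lower exposure, counts as discontinued. The Day 84 visit window is +5 days in Protocol Appendix A and ±5 days in SAP Table 2.

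**Compliance.** SAP 3.4.5 defines the total number of applications as "planned applications – # missed applications + # overdose applications" and builds the capsule total in the same way. The Table 14.3.1 footnote repeats this. Neither sets an upper limit. For the VCS, SAP 3.3.1 says "A subject will be considered compliant, if the subject administered" at least 80% of the capsules planned; it gives no formula and does not refer to 3.4.5. A footnote to Table 14.1.4 describes the excluded patients as those below 80% of the oral doses expected. On late doses, Protocol 5.4.2 says: "If it has been more than 6 hours since the planned dose time, the patient should skip the dose".

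**The concern.** The duration table is a natural place to look for how many patients took each dose for the full 12 weeks. If the programmer follows the shell, patients dosed exactly to plan are counted in a band that starts at Day 57. A patient with exactly 28 days, which is a scheduled visit day, cannot be placed at all.

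The compliance rule matters because it helps decide who is in the VCS. The per-protocol analysis on the VCS is the only sensitivity analysis that the SAP names for the co-primary endpoints (3.3.1, 3.5.1). VCS counts also decide which centers are small and must be pooled (3.5.4), and the pooled centers are the strata of the primary CMH test (3.4.6.2). If surplus capsules can offset missed ones, a patient may pass as compliant after taking fewer than 80% of the scheduled capsules.

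**Working it through.** **1. Planned capsules.** SAP 3.4.7.5 uses 84 × 2 × 6 = 1008. The kit description in Protocol 5.4 agrees: 12 weekly kits × 14 blisters × 6 capsules = 1008.

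**2. Duration of an on-schedule patient.** First dose Day 1, last dose Day 84: 84 − 1 + 1 = 84 days.

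**3. Text against shell, each duration from 1 to 91 days.**

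| Duration (days) | SAP 3.4.7.5 | Table 14.4.23 |
|---|---|---|
| 26, 27 | 26–53 | under 28 |
| 28 | 26–53 | no row |
| 54, 55, 56 | 54–83 | 29–56 |
| 84 | 84 and over | 57–84 |

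All other durations fall in corresponding bands. The text limits look deliberate: 28 − 2 = 26 and 56 − 2 = 54 are the lower ends of the Day 28 and Day 56 visit windows, and 84 is the start of the protocol's +5 window.

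**4. Who shares a row.** At 12 capsules a day, a fully dosed Day 57 stopper took 57 × 12 = 684 capsules, and 684/1008 = 67.9% exposure. The 84-day patient has 1008/1008 = 100%. The shell puts both in 57–84.

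The text bands have a weakness of the same kind. Table 14.1.3 accepts completion from Day 80, so a completer with 80–83 days would sit in 54–83 beside a Day 54 stopper: 80 × 12 = 960, or 95.2% exposure, against 54 × 12 = 648, or 64.3%. In addition, the SAP's ±5 window opens on 84 − 5 = Day 79, which Table 14.1.3 counts as discontinued.

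**5. The 80% rule under SAP 3.4.5.** Compliance = 100 × (6 × planned applications − missed capsules + overdose capsules) / (6 × planned applications). SAP 3.4.5 uses each patient's own planned applications; here I assume a full 12-week phase of 168. The limit is 0.8 × 1008 = 806.4, so 807 capsules are needed. Without overdose, at most 1008 − 807 = 201 may be missed.

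| Missed capsules | Without overdose credit | Overdose capsules needed to reach 807 | SAP 3.4.5 result |
|---|---|---|---|
| 204 | 804/1008 = 79.8% | 3 | 80.06% |
| 252 | 756/1008 = 75.0% | 51 | 80.06% |
| 402 | 606/1008 = 60.1% | 201 | 80.06% |

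The offset is one for one and has no cap.

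**6. Link to pooling.** SAP 3.5.4 calls a center small if any arm has fewer than 3 VCS patients. The plan expects 120 evaluable patients, or 40 per arm. If these are taken as the VCS, the average per arm and center is 40/14 = 2.9 with the 14 centers in SAP 2.1, or 40/17 = 2.4 with the 17 in the synopsis of protocol version 2.0. Many centers would then lie near the limit, where one patient can change the pooling.

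**The case against.** Several objections have force.

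- **The duration bands are descriptive.** They define no analysis set. A reader might infer that completers cannot be told from early stoppers. The documents do not support that: Table 14.4.23 itself splits % exposure at 80%, which separates 67.9% from 100%, and Table 14.1.3 counts Week 12 completers by arm.
- **The VCS sentence need not mean the netted formula.** An overdose capsule is not a planned capsule, and the Table 14.1.4 footnote speaks of expected doses. On that reading all three patients in the second table are excluded. This stands as far as it goes. However, 3.4.5 is the only place with a worked formula and uses the same 80% cut, so two readings remain open.
- **Overdoses have other routes to exclusion.** Protocol 5.4.2 requires deviating doses to be documented, VCS criteria may be added before unblinding, and Table 14.1.4 has a row for other major deviations. These depend on judgment at the blind data review and do not settle the formula.
- **Reclassification should be rare.** More than 201 of 1008 capsules must be missed and enough extra ones taken. Each dose is a separate six-capsule blister, and the protocol calls overdose risk low.

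A reader might also infer that the rule admits patients who took the other arm's dose. It does not follow: one 12-capsule intake in the 150 mg arm contains 300 mg, but that is not the other arm's twice-daily regimen over 84 days. A missed dose followed by a doubled one adds up to the assigned total for those two doses.

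**Conclusion.** The point holds in a limited form. The conflict between text and shell is certain. It affects seven durations, including the 84 days of every patient dosed exactly to schedule, and leaves 28 days without a row. Its effect is confined to a descriptive table, and other outputs show who completed.

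The 80% rule is inconsistent rather than plainly wrong. SAP 3.4.5 and Table 14.3.1 credit overdose capsules; SAP 3.3.1 and Table 14.1.4 can be read as not doing so. Under 3.4.5, a patient below 80% of scheduled capsules can count as compliant. The documents give no overdose rate, so the number affected is unknown; it is likely to be small. Membership of the full analysis set is untouched. The route to the primary analysis is indirect, through center pooling, and nothing in the documents shows that the result would change materially. All p-values are descriptive in any case. Both matters are worth settling before unblinding because they are cheap to correct.

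**What to change.** **Duration.** Replace the bands in Table 14.4.23 with one exhaustive set based on SAP 3.4.7.5, and use the same set in both places. First reconcile the Day 84 window between protocol and SAP, then make the lower limit of the top band agree with it and with Table 14.1.3. If the day-80 completion rule is kept, the bands become under 26, 26–53, 54–79, and 80 or more days, so that completers at 80–83 days are not grouped with Day 54 stoppers.

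**Compliance.** For the VCS criterion and the sufficient-compliance category, use

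100 × (6 × planned applications − missed capsules) / (6 × planned applications),

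with no credit for overdose. Cite this formula in SAP 3.3.1 and put the Table 14.1.4 footnote on the same capsule basis. Report overdose capsules on their own line, review them at the blind data review meeting as a separate deviation, and keep them in total exposure.

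**Cost.** Wording in the SAP and shells and a few lines of code; missed and overdose counts are already separate inputs. The downside is that a few more patients may leave the VCS, which could also alter the center pooling.
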